5.1.1. Dose Frequency

Participants will receive the voxelotor dosage form orally QD. If a participant misses a dose, the participant should resume normal dosing the next day (ie, the dose, on the day after the day of a missed dose, should not be increased or decreased).

5.1.2. Dose Modification

Participants should adhere to the dose level assigned to them.

For AEs that affect safety and tolerability, a trial of reducing or holding the dose may be used. All instances of study drug dose modification (dose reduction, interruption, or discontinuation) should be documented in the participants' medical record and recorded on the eCRF. If the condition/event leading to the dose modification has resolved, the original dose level should be resumed, unless in the judgment of the Investigator this cannot be done safely. Dose reductions due to AEs are provided in Table 3 for participants < 12 years of age and Table 5 for participants ≥ 12 years of age.

When participants switch to the modified dose of dispersible tablet, they will be asked to report any AEs to the clinical site, regardless of when the event occurs relative to the first day of switching to the modified dose. The investigator will determine, based on the participant's reporting of the event, whether a dose decrease is warranted.

Participants with a dose decrease due to an AE should be contacted by the site every 7 days (\pm 2 days) for follow-up of the AE until the new dose is deemed tolerable; at which time the Investigator may attempt to return to the prior dose or maintain the participant at the lowered dose.

Table 3: Weight-Based Dose Reductions for Participants < 12 years of Age Receiving Voxelotor Powder for Oral Suspension

Weight	Voxelotor 1500 mg Dose Equivalent	Dose Reduction 1 New Dose	Dose Reduction 2 New Dose
5 to < 10 kg	400 mg	300 mg	NA
10 to < 20 kg	600 mg	400 mg	300 mg
20 to < 40 kg	900 mg	600 mg	400 mg
\geq 40 kg $^{\rm a}$	1500 mg	1000 mg	500 mg

Abbreviations: NA, not applicable.

Note: All participants \geq 12 years of age will take voxelotor 1500 mg administered as tablets, regardless of their weight.

Table 4: Weight-Based Dose Reductions for Participants < 12 Years of Age Receiving Voxelotor Dispersible Tablet

Weight	Voxelotor 1500 mg Dose Equivalent	Dose Reduction 1 New Dose	Dose Reduction 2 New Dose
5 to < 10 kg	500 mg	300 mg	200 mg
10 to < 20 kg	800 mg	500 mg	300 mg
20 to < 40 kg	1200 mg	900 mg	300 mg
≥ 40 kg ^a	1500 mg	1000 mg	500 mg

Note: All participants ≥ 12 years of age will take voxelotor 1500 mg administered as tablets, regardless of their weight.

Table 5: Dose Reductions for Participants ≥ 12 years of Age Receiving Voxelotor Tablets

Initial Dose	Dose Reduction 1 New Dose	Dose Reduction 2 New Dose
1500 mg ^a	1000 mg	500 mg

^a Voxelotor will be administered as 500 mg tablets.

Guidelines for dose reduction, hold, or permanent discontinuation of study drug for study drug-related AEs are provided in Table 6. If the AE resolves after a dose reduction, participants may resume study drug at the original dose, subject to the Investigator's discretion. The Medical Monitor may be consulted as needed regarding dose modifications.

^a Voxelotor will be administered as 500 mg tablets.

^a Voxelotor will be administered as 500 mg tablets.

Table 6: Dose Modification Guidelines for Study Drug-Related Adverse Events

Dose Reduction				
Event	Recommended Action			
Grade ≥ 2 (NCI grading scale) AE deemed considered related to study drug by the Investigator AND Precludes continued dosing at the current dose level due to safety concern or lack of tolerability (in the Investigator's judgment)	Study drug: May be reduced by one dose reduction. If, in the opinion of the Investigator, a Grade 2 AE has resolved to ≤ Grade 1, participant may resume study drug at the original dose. If, in the opinion of the Investigator, the AE poses a significant safety concern such that a dose hold is considered, the Investigator should contact the Medical Monitor.			
ALT ≥ 3 × ULN if ALT within normal limits at baseline OR > 3 × ULN AND a ≥ 2-fold increase above baseline value if elevated ALT value at baseline in the absence of additional signs of compromised liver function such as elevated PT, PTT, INR, elevated conjugated bilirubin, jaundice, or hepatic pain	Study drug: Confirm by repeat testing within 48 to 72 hours if possible, then repeat liver panel at least weekly until ALT level improves. Additional Actions: If ALT level continues to increase, reduce dose by one dose reduction and notify the Medical Monitor.			
ALT \geq 5 × and < 8 × ULN (confirmed by repeat testing within 48 to 72 hours) in the absence of additional signs of compromised liver function such as elevated PT, PTT, elevated conjugated bilirubin, jaundice, or hepatic pain	Study drug: Reduce dose by one dose reduction. Additional actions: Repeat liver panel test within 48 to 72 hours if possible and then at least weekly until resolution to < 5 × ULN; if ALT does not improve within 2 weeks of dose reduction, the Medical Monitor should be notified. If ALT continues to increase within 1 week after a dose reduction, dose should be interrupted, and the Medical Monitor should be notified.			
Dose Interruption (Hold)	Dose Interruption (Hold)			
Event	Recommended Action			
Grade ≥ 3 (NCI grading scale) AE deemed considered related to study drug by the Investigator AND Precludes continued dosing at the current or at a reduced dose level due to safety concern or lack of tolerability in the Investigator's judgment	Study drug: Hold dose until ≤ Grade 2, then resume study drug at original dose. If, in the opinion of the Investigator, dosing should be resumed at a lower dose, contact the Medical Monitor for further discussion. If the AE recurs or worsens, reduce dose by one dose reduction. Maximum dose hold is 5 continuous days. If, in the opinion of the Investigator, a longer dose hold is clinically needed, the Medical Monitor should be contacted for discussion.			
NOTE: Study drug-related rash Grade 2 study drug-related rash that persists after a dose reduction	Management: Consider antihistamines, topical steroids, as clinically indicated. Study Drug: If rash does not resolve or improve to Grade 1 after a dose reduction, consider a dose hold. Once the rash has resolved or improved, dosing may be resumed at the reduced level or if, in the opinion of the Investigator, participant may resume study drug at the original dose. The Medical Monitor may be contacted for further discussion. Maximum dose hold is 5 continuous days. If, in the opinion of the Investigator, a longer dose hold is clinically needed, the Medical Monitor should be contacted for discussion.			

Drug Discontinuation		
Event	Recommended Action	
Grade ≥ 3 study drug-related AE that, at the discretion of the Investigator, warrants discontinuation of study drug (eg, has not improved or resolved after dose hold or reduction).	Study drug: Discontinue study drug. If the Investigator considers that the participant would benefit from continuing treatment, the Medical Monitor should be contacted.	
 Consider drug discontinuation if: ALT > 8 × ULN ALT > 3 × ULN or ≥ 2-fold increase above baseline value if elevated ALT value at baseline with additional signs of compromised liver function such as elevated PT, PTT, INR, elevated conjugated bilirubin, jaundice, or hepatic pain, appearance of fatigue, nausea, vomiting, right upper quadrant pain or tenderness, fever, rash, and/or eosinophilia. 	Study drug: Hold dose, confirm by repeat testing within 48 to 72 hours if possible, and assess potential reversible causes of liver function test abnormalities. Contact the Medical Monitor for discussion of study drug discontinuation.	

Abbreviations: AE, adverse event; ALT, alanine aminotransferase; INR, international normalized ratio; NCI, National Cancer Institute; PT, prothrombin time; PTT, partial thromboplastin time; ULN, upper limit of normal.

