5. TREATMENTS ADMINISTERED

5.1. Treatments Administered

All participants will receive voxelotor QD, administered orally as tablets, dispersible tablets, or a powder for oral suspension dosage form (packaged as stick packs).

Participants aged \geq 12 years will receive a voxelotor dose of 1500 mg QD administered as 3×500 mg tablets regardless of their body weight.

Participants aged < 12 years will receive a voxelotor dose based on their body weight to provide exposure corresponding to the adult dose of 1500 mg QD. The participant's weight at study entry will be used to determine their starting voxelotor dose in this study, as indicated in Table 1 and Table 2. The dose should be adjusted if the participant's weight increases or decreases at a scheduled clinic visit. The participant's weight will be measured according to the Schedule of Assessments (Appendix A), and dose adjustments made as needed and as indicated in Table 1 and Table 2.

The 1500 mg-equivalent dose in participants aged < 12 years will be administered as powder for oral suspension or as dispersible tablets based on the availability of each formulation.

A bioequivalence study in healthy volunteers (Study GBT-0119) comparing the voxelotor powder for oral suspension and dispersible tablet dosage forms showed that a single dose of the powder for oral suspension had an approximately 35% greater exposure than the same mg dose of dispersible tablets. Therefore, for all participants taking dispersible tablets in this study, the dose of the dispersible tablets will be increased by approximately 35%. This increase allows for a dose adjustment for the dispersible tablets ensuring that all participants taking the dispersible tablet dosage form receive the same exposure as participants receiving the powder for oral suspension dosage form (Table 1 and Table 2).

All participants < 12 years of age will receive the doses shown in Table 1 until sites are instructed by the Sponsor to switch these participants to the modified dispersible tablet doses shown in Table 2 at their next regularly scheduled visit (Appendix A). The date of the switch will be recorded on the dosing electronic case report form (eCRF).

Table 1: Voxelotor (Powder for Oral Suspension or Dispersible Tablet) Weight-Based Doses for Participants Less than 12 Years of Age

Weight	1500 mg-Equivalent Adult Dose
5 to < 10 kg	400 mg
10 to < 20 kg	600 mg
20 to < 40 kg	900 mg
≥ 40 kg ^a	1500 mg

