Note: All participants ≥ 12 years of age will take voxelotor 1500 mg administered as tablets, regardless of their weight.

^a Voxelotor will be administered as 500 mg tablets.

Table 2: Modified Dispersible Tablet Voxelotor Weight-Based Doses for Participants Less than 12 Years of Age

Population	1500 mg-Equivalent Adult Dose
5 to < 10 kg	500 mg
10 to < 20 kg	800 mg
20 to < 40 kg	1200 mg

Note: All participants ≥ 12 years of age will take voxelotor 1500 mg administered as tablets, regardless of their weight. All participants ≤ 12 years of age and ≥ 40 kg will take voxelotor 1500 mg administered as tablets.

Participants receiving a voxelotor dose of 1500 mg QD, regardless of age or weight, will receive tablets.

All dosage forms of voxelotor may be taken with or without food. Voxelotor tablets should be swallowed whole. Voxelotor dispersible tablets should be dispersed in liquid. Likewise, the powder for oral suspension dosage form should be mixed with liquid. Details regarding preparation of voxelotor for administration are provided in the Pharmacy Manual (provided separately).

Detailed instructions for study drug administration will be provided to participants and their caregivers/legal guardians, as needed.

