Note: The last dose of voxelotor should be taken 24 hours (\pm 1 hour) before PK sampling. The participant or their caregiver are to record the time of the voxelotor dose taken prior to each of these visits.

CONFIDENTIAL 58

^a Once the modified dose DT is available, switching to the modified dose DT will begin for subjects starting this study after completion of their parent study. For subjects that are already enrolled on this study, switching will begin at the subject's next scheduled visit (eg, Week 12, Week 24, etc.).

^b Safety assessments include AE and SAE monitoring, protocol-specified hematology and serum chemistry tests, abbreviated PEs, and protocol-specified vital sign measurements.

Appendix C. LIVER SAFETY: SUGGESTED ACTIONS AND FOLLOW-UP ASSESSMENTS [AND STUDY DRUG RECHALLENGE GUIDELINES]

This appendix is included to support Study transition to Pfizer Pharmacovigilance processes and systems.

Potential Cases of Drug-Induced Liver Injury

Humans exposed to a drug who show no sign of liver injury (as determined by elevations in transaminases) are termed "tolerators," while those who show transient liver injury but adapt are termed "adaptors." In some participants, transaminase elevations are a harbinger of a more serious potential outcome. These participants fail to adapt and therefore are "susceptible" to progressive and serious liver injury, commonly referred to as DILI. Participants who experience a transaminase elevation above 3 × the upper limit of normal (ULN) should be monitored more frequently to determine if they are "adaptors" or are "susceptible."

Liver function tests (LFTs) are not required as a routine safety monitoring procedure in this study. However, should an investigator deem it necessary to assess LFTs because a participant presents with clinical signs/symptoms, such LFT results should be managed and followed as described below.

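### Protocol 5.1.2 sends every child under 12 to the powder reduction table (Table 3) and never cites Table 4, so text and captions give different reduced doses for children on dispersible tablets

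*Protocol*

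**What the plan says.** Protocol 5.1.2 tells sites where to find dose reductions for adverse events: "Dose reductions due to AEs are provided in Table 3 for participants < 12 years of age and Table 5 for participants" aged 12 or over. It makes no distinction by formulation.

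The captions do make one. Table 3 is titled "Weight-Based Dose Reductions for Participants < 12 years of Age Receiving Voxelotor Powder for Oral Suspension". Table 4 is titled "Weight-Based Dose Reductions for Participants < 12 Years of Age Receiving Voxelotor Dispersible Tablet". Table 4 appears only under its own caption and in the List of Tables; no running text refers to it.

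Two sets of full doses apply to children under 12. Table 1 (section 5.1) covers powder or dispersible tablets, with 500 mg tablets at 40 kg and above. Table 2 is the "Modified Dispersible Tablet Voxelotor Weight-Based Doses for Participants Less than 12 Years of Age". The order of use is given in 5.1: "All participants < 12 years of age will receive the doses shown in Table 1 until sites are instructed by the Sponsor to switch" them to the Table 2 doses at their next scheduled visit. Appendix B, note a, adds: "Once the modified dose DT is available, switching to the modified dose DT will begin for subjects starting this study" after their parent study, with children already enrolled following at their next scheduled visit.

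Table 6 then refers to a reduction step without saying which table defines it. For confirmed ALT of 5 to <8 × ULN without other signs of compromised liver function, the action is "Study drug: Reduce dose by one dose reduction".

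**The concern.** The sentence and the captions conflict for every child under 40 kg on dispersible tablets, and neither is right throughout. The sentence fails children on the modified dose, because Table 3 starts from the lower Table 1 doses. The captions fail children on dispersible tablets who have not yet been switched, because Table 4 starts from the higher Table 2 doses.

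The children on the modified dose are also those in whom the protocol expects reductions to be considered. The next paragraph of 5.1.2 says: "When participants switch to the modified dose of dispersible tablet, they will be asked to report any AEs to the clinical site", after which the investigator decides whether a decrease is warranted. At stake is the dose given to a young child who has just had an adverse event: a first cut twice as large as intended in one weight band, or no cut at all in a pre-switch child. It also leaves unclear which dose counts as protocol-defined for the overdose and medication-error rules in 7.5 and 7.7.

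**Working it through.** **Inputs.** Full doses come from Tables 1 and 2 (Protocol 5.1), and reduction steps from Tables 3 and 4 (Protocol 5.1.2).

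**1. Reproduce the modified doses.** Section 5.1 raises the dispersible-tablet dose by about 35%:
- 400 × 1.35 = 540 mg (Table 2: 500 mg)
- 600 × 1.35 = 810 mg (Table 2: 800 mg)
- 900 × 1.35 = 1215 mg (Table 2: 1200 mg)

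These agree with Table 2 after rounding to tablet strengths. The full-dose column of Table 4 (500/800/1200 mg) is the Table 2 set, and that of Table 3 (400/600/900 mg) is the Table 1 set.

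**2. Compare the reduction entries (step 1 / step 2, mg).**

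| Weight | Table 3 | Table 4 | Entries that differ |
|---|---|---|---|
| 5 to <10 kg | 300 / NA | 300 / 200 | step 2 |
| 10 to <20 kg | 400 / 300 | 500 / 300 | step 1 |
| 20 to <40 kg | 600 / 400 | 900 / 300 | both |
| ≥40 kg | 1000 / 500 | 1000 / 500 | none |

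Four of eight entries differ.

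**3. Child on modified dispersible tablets.** Cut = 1 − reduced dose / full dose.

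| Weight (full dose) | Step 1, Table 3 (literal text) | Step 1, Table 4 | Step 2, Table 3 (literal text) | Step 2, Table 4 |
|---|---|---|---|---|
| 5 to <10 kg (500 mg) | 1 − 300/500 = 40% | 40% | no step | 1 − 200/500 = 60% |
| 10 to <20 kg (800 mg) | 1 − 400/800 = 50% | 1 − 500/800 = 37.5% | 1 − 300/800 = 62.5% | 62.5% |
| 20 to <40 kg (1200 mg) | 1 − 600/1200 = 50% | 1 − 900/1200 = 25% | 1 − 400/1200 = 67% | 1 − 300/1200 = 75% |

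**4. Child on dispersible tablets before the switch (Table 1 dose), step 1.**

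| Weight (full dose) | By caption (Table 4) | By the sentence (Table 3) |
|---|---|---|
| 5 to <10 kg (400 mg) | 1 − 300/400 = 25% | 25% |
| 10 to <20 kg (600 mg) | 1 − 500/600 = 17% | 1 − 400/600 = 33% |
| 20 to <40 kg (900 mg) | 1 − 900/900 = 0% | 1 − 600/900 = 33% |

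**5. Look for a rule that works for everyone.** Below 40 kg, full doses of 400, 600 and 900 mg occur only in Table 3, and 500, 800 and 1200 mg only in Table 4. At 40 kg and above the rows are identical. Choosing the table by the child's full dose therefore gives one answer in every case. The rule must use the full dose, not the dose currently taken: 900 mg is both the Table 1 full dose at 20 to <40 kg and the first reduced dose in Table 4 for that band. The protocol states no such rule.

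**The case against.** The strongest reply is that only a cross-reference is missing. Table 4 comes straight after Table 3, is clearly captioned, and starts at 1200 mg in the row concerned. The figure 1200 appears nowhere in Table 3. To reach 600 mg, a site would have to ignore Table 3's caption, overlook that its full-dose column does not fit the child, and pass over Table 4. This stands: an attentive site would probably pick the right table.

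It is also fair that the two errors need opposite readings. The 1200 to 600 mg step needs the sentence to override the captions, and the 900 to 900 mg step needs the captions to override the sentence. A reduction to the same dose would be noticed, and the pre-switch period is transitional. But when each reading is wrong for a different group, the protocol has no reading that a site can apply uniformly.

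The consequences are bounded. At step 1 the literal reading gives the same or a larger cut than Table 4, so the error is toward less drug. At step 2 it is not: 400 mg instead of 300 mg at 20 to <40 kg, and no step at 5 to <10 kg. Table 6 is guidance, the Medical Monitor may be consulted, children with a decrease are contacted every 7 days (± 2 days), and the original dose should normally be resumed on resolution.

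A reader might infer that children have been or will be misdosed, or that the safety results are compromised. The documents support neither. They report no misdosing and do not say how many children are in each group. The SAP analyses are descriptive, and its exposure summary (8.2.1) counts whether and how often doses were reduced, not by how much.

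**Conclusion.** The sentence in 5.1.2 is wrong as written and should be corrected. It is an operative paediatric dosing instruction that conflicts with the protocol's own table. Taken literally, it doubles the first cut at 20 to <40 kg (50% instead of 25%), enlarges it at 10 to <20 kg (50% instead of 37.5%), gives too small a second cut at 20 to <40 kg (67% instead of 75%) and leaves no second step at 5 to <10 kg. Reading by caption gives no first-step cut for a pre-switch child on 900 mg.

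The likelihood of error in practice is low, for the reasons given above. Nor does the point mean that any tabulated dose is wrong: both tables are usable once it is clear who belongs to which. The conclusion assumes that Table 4 was meant for the Table 2 doses, as its full-dose column indicates, and that no separate document, such as the Pharmacy Manual (not available here), already tells sites how to choose.

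**What to change.** Replace the sentence in 5.1.2 with wording to this effect:

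> The reduction table for an AE is chosen by the participant's assigned full (unreduced) dose. Under 12 years with a full dose from Table 1 (powder, dispersible tablets, or 500 mg tablets if ≥40 kg): use Table 3. Under 12 years with a full dose from Table 2 (modified dispersible tablets): use Table 4. Aged 12 years or over: use Table 5.

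Retitle Table 3 to cover all Table 1 doses, and Table 4 to say modified dispersible tablets, the term Table 2 already uses. Naming the 500 mg tablets keeps children under 12 who weigh 40 kg or more assigned to a table. Using the full dose keeps a child already reduced from 1200 to 900 mg in Table 4 for the second step (300 mg).

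No tabulated dose changes. The Table 3 steps below 40 kg (300, 400 and 600 mg) can be made from the 100 and 300 mg dispersible tablets in section 5.3; 400 mg needs the 100 mg strength.

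The cost is one sentence and two titles. Because the text governs paediatric dosing, it needs a protocol amendment or clarification with IRB/EC approval (Protocol 11.1 and 11.4) and a notice to sites. It could travel with the next amendment.

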In the majority of DILI cases, elevations in AST (aspartate transaminase) and/or ALT (alanine transaminase) precede total bilirubin elevations (> 2 × ULN) by several days or weeks. The increase in total bilirubin typically occurs while AST/ALT is/are still elevated above 3 × ULN (ie, AST/ALT and total bilirubin values will be elevated within the same laboratory sample). In rare instances, by the time total bilirubin elevations are detected, AST/ALT values might have decreased. This occurrence is still regarded as a potential DILI. Therefore, abnormal elevations in either AST or ALT in addition to total bilirubin that meet the criteria outlined below are considered potential DILI (assessed per Hy's law criteria) cases and should always be considered important medical events, even before all other possible causes of liver injury have been excluded.

The threshold of laboratory abnormalities for a potential DILI case depends on the participant's individual baseline values and underlying conditions. Participants who present with the following laboratory abnormalities should be evaluated further as potential DILI (Hy's law) cases to definitively determine the etiology of the abnormal laboratory values:

- Participants with AST/ALT and total bilirubin values within the normal range who subsequently present with AST/ALT values $\geq 3 \times \text{ULN}$ AND a total bilirubin value $\geq 2 \times \text{ULN}$ with no evidence of hemolysis and an alkaline phosphatase value $\leq 2 \times \text{ULN}$ or not available.
- For participants with baseline AST **OR** ALT **OR** total bilirubin values above the ULN, the following threshold values are used in the definition mentioned above, as needed, depending on which values are above the ULN at baseline:
 - O Preexisting AST/ALT baseline values above the normal range: AST/ALT values ≥ 2 times the baseline values AND $\geq 3 \times \text{ULN}$; or $\geq 8 \times \text{ULN}$ (whichever is smaller).

O Preexisting values of total bilirubin above the normal range: total bilirubin level increased from baseline value by an amount of $\geq 1 \times ULN$ or if the value reaches $\geq 3 \times ULN$ (whichever is smaller).

Rises in AST/ALT and total bilirubin separated by more than a few weeks should be assessed individually based on clinical judgment; any case where uncertainty remains as to whether it represents a potential Hy's law case should be reviewed with the sponsor.

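### Table 6 leaves out two exact ALT values: 8.0 × ULN without liver signs, and 3.0 × ULN with liver signs and a normal baseline

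*Protocol*

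**What the plan says.** All the ALT rows are in Protocol Section 5.1.2, Table 6.

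- **Retest row (dose-reduction part).** For a normal baseline: "ALT ≥ 3 × ULN if ALT within normal limits at baseline". For an elevated baseline: "> 3 × ULN AND a ≥ 2-fold increase above baseline value if elevated ALT value at baseline". The row is restricted to participants without additional signs of compromised liver function and has no upper ALT limit. The action is to repeat the tests, and to reduce the dose if ALT keeps rising.
- **Reduction row (dose-reduction part).** ALT from 5 × ULN inclusive up to "< 8 × ULN (confirmed by repeat testing within 48 to 72 hours) in the absence of additional signs of compromised liver function". The action is one dose reduction.
- **Hold row (drug-discontinuation part).** Two criteria lead to it. The first is "Consider drug discontinuation if: ALT > 8 × ULN", with or without signs. The second, which requires liver signs, is "ALT > 3 × ULN or ≥ 2-fold increase above baseline value if elevated ALT value at baseline with additional signs". The action begins "Hold dose, confirm by repeat testing within 48 to 72 hours if possible" and includes contacting the Medical Monitor about discontinuation.

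Appendix C sets separate limits for reporting potential drug-induced liver injury. They are inclusive (≥ 3 × ULN for a normal baseline, with a ≥ 8 × ULN limb for an elevated one), but they also require raised bilirubin and do not set the dose action.

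**The concern.** A graded safety rule should not become milder as the laboratory value rises or when liver signs appear. Table 6 as printed does both, once each. At 8.0 × ULN a site following the text exactly does less than at a confirmed 7.9. At 3.0 × ULN with a normal baseline, the text prescribes a retest for a participant without signs and offers no ALT row for one with signs.

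A further wording question concerns the with-signs criterion. The retest row separates normal from elevated baselines and joins its two elevated-baseline conditions with *and*. The with-signs criterion joins its conditions with *or* and does not say whether the 3 × ULN arm applies to someone whose baseline was already raised. Sites could therefore act differently on the same result.

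**Working it through.** The plan states no figure to reproduce. The check codes the ALT rows as printed, with values in multiples of ULN and a baseline of 1.0 or less counted as normal.

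**Rules (x = ALT, b = baseline)**

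- Retest: no signs, and either b ≤ 1 with x ≥ 3, or b > 1 with x > 3 and x/b ≥ 2.
- Reduce: no signs, and 5 ≤ x < 8, confirmed.
- Hold: x > 8; or signs with x > 3 or (b > 1 and x/b ≥ 2), taking the *or* literally.

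**Step 1: 8.0 without signs, confirmed values**

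| Baseline | ALT 7.9 | ALT 8.0 | ALT 8.1 |
|---|---|---|---|
| Normal | reduce | retest only | hold |
| 4.0 | reduce | retest only (8.0/4.0 = 2.0-fold) | hold |
| 4.1 | reduce | no ALT row (8.0/4.1 = 1.95-fold) | hold |

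The retest row drops out at 8.0 when 8.0/b < 2, that is, when b > 4.

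**Step 2: 3.0 with a normal baseline**

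- No signs: 3.0 ≥ 3, so retest.
- Signs: the retest row is closed and 3.0 is not above 3, so no ALT row.
- Signs at 3.1: hold.

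**Step 3: is the problem confined to these values?** The rules were run over ALT 0.1 to 12.0 and baseline 0.5 to 8.0 in steps of 0.1, with and without signs. On the literal reading, the action becomes milder as ALT rises only at 8.0 without signs, for all 76 baselines. Signs give a milder action than no signs only at 3.0, for the 6 normal baselines (0.5 to 1.0). With both limits made inclusive, the counts are 0 and 0, and the only changed actions are at those two values.

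**Step 4: the *or* for an elevated baseline.** Three readings are possible: literal (above 3 × ULN applies to everyone), split by baseline (at least 2-fold if elevated), and *and* (both conditions if elevated, as in the retest row).

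| Baseline, ALT, with signs | Literal | Split | And |
|---|---|---|---|
| 3.5, 6.0 (6.0/3.5 = 1.71-fold) | hold | no ALT row | no ALT row |
| 1.2, 2.5 (2.5/1.2 = 2.08-fold) | hold | hold | no ALT row |
| 5.0, 3.1 (below own baseline) | hold | no ALT row | no ALT row |

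In the first line, a participant without signs and with a confirmed 6.0 is reduced. Under the split or *and* reading, the participant with signs gets the milder handling. This needs 5 ≤ x < 2b, so it can arise only when b > 2.5.

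**The case against.** Several points limit the concern, and most of them stand.

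- **Exact equality is rare.** The reduction row needs a confirmed value. A first 7.9 and a first 8.0 with a normal baseline and no signs both start with a retest, and the two paths diverge only if the repeat is again exactly 8.0. This stands, and it makes the gap small.
- **The 3.0 gap depends on parsing.** It assumes that the restriction to participants without signs covers both limbs of the retest row. That is the natural reading. If the restriction covered only the elevated-baseline limb, the retest row would catch 3.0 with signs.
- **Liver signs are not one list.** The drug-discontinuation part adds symptoms such as fatigue, fever and rash that the retest row does not name. The 3.0 gap is clear only for signs named in the retest row, such as jaundice or a raised INR.
- **Other guidance remains.** Table 6 is a guideline. Its general rows for drug-related events of Grade 2 or 3 and above allow a reduction or hold, the Medical Monitor may be consulted, and Appendix C asks for closer monitoring above 3 × ULN. This limits harm, but the general rows depend on relatedness and investigator judgment and do not close the gaps.
- **The symbols come from a PDF.** A misread inequality sign cannot be excluded. The *or* versus *and* question does not depend on this.

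A reader might infer that participants at 8.0 × ULN are left without any rule, or that Table 6 contradicts Appendix C. The documents support neither. The retest row has no upper limit, so 8.0 is wholly uncovered only when baseline exceeds 4 × ULN. Appendix C's limits ("Participants with AST/ALT and total bilirubin values within the normal range who subsequently present with AST/ALT values" and "Preexisting AST/ALT baseline values above the normal range: AST/ALT values ≥ 2 times the baseline values AND" open the two cases) classify potential liver injury together with bilirubin and do not direct dosing.

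**Conclusion.** The two boundary gaps are wrong as written and minor. They are single values, no endpoint or analysis depends on them, and the documents do not show how many participants would meet them. The conclusion rests on the inequality signs as printed, on confirmed values at 8.0, and, at 3.0, on the natural reading of the retest row and on signs that row names.

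The *or* is a secondary request for clarification, on which the main point does not depend. A reader might infer that the different connective is itself an error. That does not follow, because a lower trigger when liver signs are present is coherent, and the literal text can be applied. Nor is the literal reading plainly the right one. It avoids milder handling of participants with signs, but it also holds a participant whose ALT is above 3 × ULN yet below his or her own elevated baseline. The choice belongs to the sponsor and should be stated.

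**What to change.** In the drug-discontinuation part of Table 6:

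1. Change the first criterion from above 8 × ULN to ≥ 8 × ULN.
2. Change the with-signs limit for a normal baseline from above 3 × ULN to ≥ 3 × ULN.
3. State separately what applies with signs when baseline ALT is elevated, choosing among the three readings. If the split or *and* reading is intended, add a rule so that a participant with signs is not handled more mildly than one without.

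Changes 1 and 2 add a temporary hold, a retest and Medical Monitor contact at those exact values only. The effect of change 3 depends on the reading chosen and on what sites do now. No scheduled test or visit is added. The wording can go into the next amendment, with the approvals described in Protocol Sections 11.1 and 11.4.
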